Comprehensive Cancer Center of Wake Forest University
A Pilot Study: Open-Label Clinical Trial of CPI-613 in Patients with Advanced Bile Duct
Cancers
CCCWFU # 59212

Principal Investigator: [name] [name]
Section on Hematology and Oncology
Wake Forest School of Medicine
[name]
[name]

Co-Investigators: A. [name]
Department of Radiation Oncology
Wake Forest School of Medicine

Biostatistician: [name], PhD
Division of Public Health Sciences
Comprehensive Cancer Center of Wake Forest University

Research Nurse: [name] [name]
Comprehensive Cancer Center of Wake Forest University

Data Manager: [name]
Comprehensive Cancer Center of Wake Forest University

Regulatory / Budget: [name]
Comprehensive Cancer Center of Wake Forest University

Investigational Drug: CPI-613

IND Number: 117,500

Drug Sponsor: Cornerstone Pharmaceuticals, Inc.

Version Date: 07.16.18
02.28.18
02.22.17
02.16.16
10.22.15
06.16.15

Comprehensive Cancer Center of Wake Forest University
A Pilot Study: Open-Label Clinical Trial of CPI-613 in Patients with Advanced Bile Duct
Cancers
CCCWFU # 59212

[figure not shown]
04.23.15
01.21.15
11.14.14
09.08.14
07.24.14
06.19.14
05.20.14
02.28.14
08.16.13
07.16.13
04.23.13
04.05.13
02.08.13
02.04.13
12.19.12

Proprietary and Confidential

SCHEMA

Patients with histologically
and cytologically proven
bile duct cancer

Comprehensive Cancer Center of Wake Forest University
A Pilot Study: Open-Label Clinical Trial of CPI-613 in Patients with Advanced Bile Duct
Cancers
CCCWFU # 59212

Primary Objective

To evaluate the safety and anti-cancer activities (assessed based on Response Rate) of CPI-613 in patients with advanced unresectable bile duct cancer who have failed available therapies.

Secondary Outcome measures

- Progression-free survival
- Overall Survival

Design

Open-label single arm

* Maximum number of cycles allowed is 12, unless the investigator considers additional treatment can provide clinical benefit

** Two additional cycles will not be given if the patient no longer meets eligibility criteria, has worsening of biliary function, or has symptomatic progression.

Comprehensive Cancer Center of Wake Forest University
A Pilot Study: Open-Label Clinical Trial of CPI-613 in Patients with Advanced Bile Duct
Cancers
CCCWFU # 59212

Table of Contents

1. BACKGROUND AND STUDY OBJECTIVES.....	6
2. STUDY DESIGN.....	7
2.1 Study Objective.....	7
2.2 Outcome Measures.....	7

1. BACKGROUND AND STUDY OBJECTIVES

Biliary duct carcinoma is a rare but highly fatal malignancy. Estimated incidence of bile duct and gallbladder cancer approached 10,000 cases in 2009, with nearly 3,400 estimated deaths according to the American Cancer Society.

Cholangiocarcinoma is an epithelial cancer of the biliary duct system that may originate in the liver and extrahepatic bile ducts, which may terminate at the ampulla of Vater. Based on anatomical location, cholangiocarcinoma can be divided into 3 categories: (1) intrahepatic (20-25%), occurring in the bile ducts residing within the liver; (2) extrahepatic or perihilar (also known as Klatskin tumour, 50%), occurring at the confluence of the right and left hepatic ducts; and (3) distal extrahepatic bile duct (20-25%), occurring beyond the liver. More than 90% of cholangiocarcinoma are adenocarcinomas, with different histological variants including adenocarcinoma, papillary adenocarcinoma, intestinal-type adenocarcinoma, and mucinous adenocarcinoma.

Conventional chemotherapy and radiation therapy have not been shown to be effective in prolonging long-term survival. Although photodynamic therapy has been reported to be effective as a palliative treatment, it is not curative. Radical surgery is the only potentially curative treatment modality. However, in most cases, the tumors are well advanced at the time of diagnosis, which results in limited treatment options. The impact of chemotherapy on survival remains controversial. The overall survival for patients with cholangiocarcinoma is ~6 months.

Gemcitabine, with or without cisplatin, is the first line chemotherapy. However, the outcomes of this therapy are limited. After gemcitabine/cisplatin therapy, there is essentially no known effective chemotherapy. The poor response of cholangiocarcinoma to current therapy highlights the need for a safe and effective therapy.

CPI-613 is a novel anti-cancer agent (Zachar et al. 2011). CPI-613 selectively targets the altered form of mitochondrial energy metabolism in tumor cells, causing changes in mitochondrial enzyme activities and redox status which leads to apoptosis, necrosis and autophagy of tumor cells (Zachar et al. 2011). The activities of CPI-613 involve the catalytic and regulatory functions of the altered form of the pyruvate dehydrogenase complex (PDC) and the α -ketoglutarate dehydrogenase complex (KGDHC) found in tumor cells (Zachar et al. 2011). CPI-613 is also well-tolerated at doses up to 3,000 mg/m², according to Phase 1 trials in patients with solid tumors and hematologic malignancies. Although it has not been investigated in patients with cholangiocarcinoma, CPI-613 has exhibited anti-cancer activities against a variety of advanced cancers including different types of solid tumors (Lee et al. 2011 & 2012; Senzer et al. 2012) and hematologic malignancies (Pardee et al, 2011a and b, & 2012). Therefore, the anti-cancer activities and safety of CPI-613 against advanced bile duct cancers are investigated in this study. Interestingly, after the first two cycles of treatment, the radiologic response by CAT scan or PET scan did not correlate well with the clinical response for various tumor types, and patients had increased survival despite pseudo-progression on their initial scan. One of the reasons is that CPI-613 seems to be producing an inflammatory and necrotic local effect that can

Comprehensive Cancer Center of Wake Forest University
A Pilot Study: Open-Label Clinical Trial of CPI-613 in Patients with Advanced Bile Duct
Cancers
CCCWFU # 59212

be read as pseudo-progression on a standard CT. For this reason, we will allow patients to continue for an additional two cycles even if the first treatment scan shows progression of disease by RECIST criteria. After 2 additional cycles, we expect to understand if the patient responded to therapy or not as the inflammatory/necrotic effect should have subsided. Allowing 2 additional treatment cycles with Disease Progression according to RECIST cannot take place if any of the following conditions occur:

- the patient no longer meets eligibility criteria set at the start of the protocol (see Section 3.)
- worsening of biliary function when compared to baseline
- the patient has symptomatic progression

2. STUDY DESIGN

2.1 Study Objective

The objective of this study is to evaluate the safety and efficacy of CPI-613 in patients with advanced unresectable bile duct cancers who have failed available therapies.

2.2 Outcome Measures

The primary outcome measures are safety and anti-cancer activities (assessed based on Response Rate [RR]).

The secondary outcome measures are:

- Progression-Free-Survival (PFS).
- Overall Survival (OS).

2.3 Open-Label Single-Arm Study Design

This is an open-label study, and investigators and subjects are not blinded to the treatment. Also, the assignment of patients will not be randomized, since there is only a single arm in this study.

3.0 PATIENT ELIGIBILITY CRITERIA

3.1 Inclusion Criteria

Patients must meet all of the following inclusion criteria before enrollment:

- A. Histologically and cytologically proven bile duct cancer of any type (including intrahepatic cholangiocarcinomas, extrahepatic primary cholangiocarcinomas, hilar cholangiocarcinomas, cholangiocarcinomas located in the gall bladder or hepatic capsule effraction, and carcinoma of the Ampulla of Vater, etc.) that is not amenable

Comprehensive Cancer Center of Wake Forest University
A Pilot Study: Open-Label Clinical Trial of CPI-613 in Patients with Advanced Bile Duct
Cancers
CCCWFU # 59212

- to surgery, radiation, or combined modality therapy with curative intent, and has failed or is not eligible for available chemotherapies such as gemcitabine with or without platinum.
- B. Local, locally-advanced, or metastatic disease documented as having shown progression on a scan (e.g., CT, MRI).
 - C. Measurable tumor according to RECIST 1.1 criteria with at least one unidimensionally measurable target lesion.
 - D. No evidence of biliary duct obstruction, unless obstruction is controlled by local treatment or, in whom the biliary tree can be decompressed by endoscopic or percutaneous stenting with subsequent reduction in bilirubin to below 1.5x Upper Level of Normal (ULN).
 - E. No acute toxic effects from previous treatment superior to grade 1 at the start of the study.
 - F. Eastern Cooperative Oncology Group (ECOG) performance status being 0-2.
 - G. Expected survival >3 months.
 - H. Male and female patients 18 years of age and older.
 - I. Women of child-bearing potential (i.e., women who are pre-menopausal or not surgically sterile) must use accepted contraceptive methods (abstinence, intrauterine device [IUD], oral contraceptive or double barrier device) during the study, and must have a negative serum or urine pregnancy test within 1 week prior to treatment initiation.
 - J. Fertile men must practice effective contraceptive methods during the study, unless documentation of infertility exists.
 - K. Laboratory values ≤ 2 weeks must be:
 - Adequate hematologic (granulocyte count $\geq 1500/\text{mm}^3$; white blood cell [WBC] ≥ 3500 cells/ mm^3 or ≥ 3.5 bil/L; platelet count $\geq 100,000$ cells/ mm^3 or ≥ 100 bil/L; absolute neutrophil count [ANC] ≥ 1500 cells/ mm^3 or ≥ 1.5 bil/L; and hemoglobin ≥ 9 g/dL or ≥ 90 g/L).
 - Adequate hepatic function (aspartate aminotransferase [AST/SGOT] ≤ 3 x upper normal limit [UNL], alanine aminotransferase [ALT/SGPT] ≤ 3 x UNL (≤ 5 x UNL if liver metastases present), bilirubin ≤ 1.5 x UNL).
 - Adequate renal function (serum creatinine ≤ 2.0 mg/dL or 177 $\mu\text{mol/L}$).
 - Adequate coagulation (“International Normalized Ratio or INR must be ≤ 1.5 ” unless on therapeutic blood thinners)
 - L. No evidence of active infection and no serious infection within the past month.
 - M. Mentally competent, ability to understand and willingness to sign the informed consent form.

3.2 Exclusion Criteria

Patients with the following characteristics are excluded:

Comprehensive Cancer Center of Wake Forest University
A Pilot Study: Open-Label Clinical Trial of CPI-613 in Patients with Advanced Bile Duct
Cancers
CCCWFU # 59212

- A. Patients receiving any other standard or investigational treatment for their cancer, or any other investigational agent for any indication within the past 2 weeks prior to initiation of CPI-613 treatment.
- B. Serious medical illness that would potentially increase patients' risk for toxicity.
- C. Any active uncontrolled bleeding, and any patients with a bleeding diathesis (e.g., active peptic ulcer disease).
- D. Pregnant women, or women of child-bearing potential not using reliable means of contraception (because the teratogenic potential of CPI-613 is unknown).
- E. Lactating females.
- F. Fertile men unwilling to practice contraceptive methods during the study period.
- G. Life expectancy less than 3 months.
- H. Any condition or abnormality which may, in the opinion of the investigator, compromise the safety of patients.
- I. Unwilling or unable to follow protocol requirements.
- J. Dyspnea with moderate exertion.
- K. Patients with clinically significant pleural or pericardial effusions.
- L. Active heart disease including but not limited to symptomatic congestive heart failure, symptomatic coronary artery disease, symptomatic angina pectoris, symptomatic myocardial infarction, or symptomatic congestive heart failure. Also patients with a history of myocardial infarction that is <1 year prior to registration, or patients with previous congestive heart failure (<1 year prior to registration) requiring pharmacologic support or with Left Ventricular Ejection Fraction <50%.
- M. A history of additional risk factors for torsade de pointes (e.g., heart failure, hypokalemia, family history of Long QT Syndrome)
- N. Evidence of active infection, or serious infection within the past month.
- O. Patients with known HIV infection.
- P. Patients with baseline troponin levels greater than the institutional limit of normal.
- Q. Patients who have received cancer immunotherapy of any type within the past 2 weeks prior to initiation of CPI-613 treatment.
- R. Requirement for immediate palliative treatment of any kind including surgery.
- S. Patients that have received a chemotherapy regimen with stem cell support in the previous 6 months.
- T. Prior illicit drug addiction.
- U. Any condition or abnormality which may, in the opinion of the investigator, compromise the safety of the patient.

3.3 Inclusion of Women and Minorities

Both men and women and members of all races and ethnic groups are eligible for participation in this trial.

4.0 REGISTRATION PROCEDURES

All patients entered on any CCCWFU trial, whether treatment, companion, or cancer control

Comprehensive Cancer Center of Wake Forest University
A Pilot Study: Open-Label Clinical Trial of CPI-613 in Patients with Advanced Bile Duct
Cancers
CCCWFU # 59212

trial, **must** be registered with the CCCWFU Protocol Registrar or entered into the Oncology Research Information System (ORIS) Screening Log within 24 hours of informed consent.

Patients **must** be registered prior to the initiation of treatment.

In order to ensure prompt registration of your patient, please:

1. Complete the Eligibility Checklist (Appendix A)
2. Complete the Protocol Registration Form (Appendix A)
3. Alert the WFUHS registrar by phone, *and then* send the signed Informed Consent Form, Eligibility Checklist and Protocol Registration Form to the registrar, either by fax or e-mail.

Contact Information:

Protocol Registrar [contact]

Protocol Registrar [contact]

Protocol Registrar E-MAIL ([contact])

*Protocol Registration is open from 8:30 AM - 4:00 PM, Monday-Friday.

4. Please fax/e-mail ALL eligibility source documents with registration. Patients **will not** be registered without all required supporting documents.

Note: If labs were performed at an outside institution, please provide a printout of the results. Please ensure that the most recent lab values are sent.

To complete the registration process, the Registrar will:

- assign a patient study number
- register the patient on the study

Comprehensive Cancer Center of Wake Forest University
A Pilot Study: Open-Label Clinical Trial of CPI-613 in Patients with Advanced Bile Duct Cancers
CCCWFU # 59212

5.0 STUDY PROCEDURES

Table 5-1 (below) provides an overview of the study procedures for the pre-study screen and pre-cycle 1 treatment period. The specifics are described in subsequent sections.

Table 5-1: Study Procedures for Pre-Study Screen and Pre-Cycle 1 Treatment Period

Assessments	Pre-Study Screen ⁸	Pre-Cycle 1 treatment (Given Only Once for Each Patient)	
		Days 1-5	Days 6-7
CPI-613 ¹		√	
Medical history	√		
Pregnancy test for women of child-bearing potential	√		
Evaluation of symptoms and vital signs	√ ³	√ ⁴	
ECOG performance status and survival	√		
Clinical chemistry, hematology and coagulation ²	√	√ ⁵	
Cardiac: Troponin I	√	√ ⁵	
Cardiac: ECG	√	√ ⁵	
CT w/ contrast (chest/abdomen/pelvis)	√		
CA-19-9	√		
Plasma CPI-613 concentrations, possibly metabolite concentrations, and possibly other analyses ⁶		√ ⁷	
Optional blood and serum samples ⁹	√		
Adverse event evaluation		√	√

ECOG = Eastern Cooperative Oncology Group; hr = hour; min = minute.

¹ CPI-613 is given as a 2-hr IV infusion via a central venous catheter.

² Specific chemistries are listed in section 5.2.2. Renal function will be assessed utilizing the Cockcroft-Gault formula. Coagulation (PT/PTT) will only be assessed at screening.

³ Other than evaluation of symptoms and vital signs, height and weight, physical exam, and medications are also determined during pre-study medical screening.

⁴ Perform on Days 1 and 4 only.

⁵ Perform on Days 1 and 5 only.

⁶ Obtained according to the following schedule: pre-dose (~5 min before dosing), and at 0.5, 1, 1.5, 2, and 4 hrs post-dose of CPI-613.

⁷ Day 1 only

⁸ Pre-study screening tests, which are also enrollment evaluations, must be performed according the following time frames:

Within 4 weeks: tumor assessment (CT w/ contrast), CA-19-9

Within 2 weeks: medical history, physical exam, vital signs, height, weight, ECG, ECOG, evaluation of symptoms and medications, clinical chemistry, hematology, coagulation, and troponin

Within 1 week: pregnancy test for women of child-bearing potential, pre-study labs and ECG obtained before enrollment may be used for Day 1

⁹ Optional blood and serum samples are for possible testing of biomarkers, predictors of biological responses, toxicity, genotype vs. drug response relationship, etc.

Comprehensive Cancer Center of Wake Forest University
A Pilot Study: Open-Label Clinical Trial of CPI-613 in Patients with Advanced Bile Duct Cancers
CCCWFU # 59212

Table 5-2 (below) provides an overview of the study procedures for all treatment cycles and the follow-up period. The specifics are described in subsequent sections.

Table 5-2: Study Procedures for All Treatment Cycles and Follow-Up Period

Assessments	Cycles 1 and 2 (Each cycle is 4 weeks)								Cycles 3 through 12 (Each cycle is 4 weeks)								Follow-Up Every 2 months until death
	Week 1		Week 2		Week 3		Week 4		Week 1		Week 2		Week 3		Week 4		
	D1	D4	D1	D4	D1	D4	D3,4,or 5		D1	D4	D1	D4	D1	D4	D3, 4, or 5		
CPI-613 ¹	√	√	√	√	√	√			√	√	√	√	√	√			
Evaluation of symptoms and vital signs	√ ²		√ ²		√ ²				√ ²		√ ²		√ ²				
ECOG performance status and survival	√ ²		√ ²		√ ²				√ ²		√ ²		√ ²				
Clinical chemistry, hematology ^{2,3,9}	√ ²	√	√	√	√	√			√ ²								
Cardiac: Troponin I and ECG ⁹	√ ²								√ ²								
CT w/ contrast (chest/abdomen/pelvis)																√ ⁴	
CA-19-9																√ ⁴	
Plasma CPI-613 concentrations, possibly metabolite concentrations, and possibly other analyses ⁶	√ ⁸																
Optional blood and serum samples ¹⁰																√ ⁴	
Phone contact																√ ⁷	

ECOG = Eastern Cooperative Oncology Group; hr = hour; min = minute; D1 = day 1; D4 = day 4.

¹ CPI-613 is given as a 2-hr IV infusion via a central venous catheter. Treatment with CPI-613 may be adjusted +/- 1 day.

² These tests are performed with results available for review within 24 hrs before administration of the anti-tumor agents.

³ Specific chemistries are listed in section 5.2.2. Renal function will be assessed utilizing the Cockcroft-Gault formula.

⁴ Performed at the following time points: during week 4 (preferably Wednesday or later) of cycle 3 for all patients. For patients without progression, perform during week 4 of cycles 6, 9, and 12. In patients where progression was detected from the cycle 3 scan, perform during week 4 of cycle 5. If patient remains on study after cycle 5, perform every 3 months thereafter.

⁶ Plasma samples will be obtained pre-dose (~5 min before dosing), and at 0.5, 1, 1.5, 2, and 4 hrs post-dose of CPI-613.

⁷ Survival and post-study cancer treatment will be monitored bimonthly via telephone contact after the patients are taken off the trial.

⁸ Cycle 1 only

⁹ Within 1 week: pre-study labs and ECG obtained before enrollment may be used for Day 1

¹⁰ Optional blood and serum samples are for possible testing of biomarkers, predictors of biological responses, toxicity, genotype vs. drug response relationship, etc.

Comprehensive Cancer Center of Wake Forest University
A Pilot Study: Open-Label Clinical Trial of CPI-613 in Patients with Advanced Bile Duct
Cancers
CCCWFU # 59212

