5.1 Pre-Study Screening Tests and Safety Assessment

5.1.1 *Pre-Study Screening Tests*

Pre-study screening tests, which are also enrollment evaluations, must be performed according the following time frames:

Within 4 weeks: tumor assessments based on contrast CT of chest, abdomen, and pelvis, and optional blood and serum samples.

Within 2 weeks: medical history, physical exam, vital signs, height, weight, ECG, ECOG, evaluation of symptoms and medications, clinical chemistry, hematology, coagulation, and troponin I.

Within 1 week: pregnancy test for women of child-bearing potential.

5.1.2 *Safety Assessment*

The safety of CPI-613 will be assessed from the first dose to 1 month after last dose of CPI-613. The assessment will be based on:

- evaluation of symptoms
- vital signs
- ECOG performance status and survival
- clinical chemistry
- renal function
- hematology
- coagulation
- cardiac safety assessments via troponin I and ECG

The specifics of the safety tests are described in Section 5.2. All safety assessment tests are performed during screening (performed within 2 weeks prior to treatment with CPI-613 during Pre-Cycle 1), on Day 5 during Pre-Cycle 1, and prior to each treatment cycle with results available for review within 24 hrs before administration the anti-tumor agents. Chemistries, hematology, and renal function will also be performed on Days 1 and 4 of each treatment week during the first 2 cycles. ECOG performance status and survival will be assessed on Day 1 of each treatment week.

5.1.3 *Tumor Assessment*

Tumor response to treatment will assessed at baseline, and initially after the time frame encompassing the pre-cycle 1 treatment and the first three cycles using

Comprehensive Cancer Center of Wake Forest University
A Pilot Study: Open-Label Clinical Trial of CPI-613 in Patients with Advanced Bile Duct
Cancers
CCCWFU # 59212

contrast CT of the chest, abdomen and pelvis as well as serum levels of tumor marker CA-19-9 and performance status. Should the principal investigator determine that tumor progression has occurred the patient will be removed from the study. Should the principal investigator determine that the patient has stable disease or has had a favorable response, those patients will continue treatment with CPI-613 for an additional three cycles (approximately three months). At that time, patients will then undergo re-imaging contrast CT, CA-19-9 and performance status.

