Pseudoprogession will be ruled out by allowing patients to receive the study drug for another 2 cycles after the first response assessment before making definitive assessment of progression or response. However, patients will not be allowed to continue treatment with CPI-613 at the time of “pseudo-progression” if any of the following criteria are met:

- a. The patient does not meet eligibility criteria set at the start of the protocol.
- b. Biliary function worsens.
- c. The patient has symptomatic progression.

OS will be determined from the first dose of CPI-613 to death, assessed up to 3 years after the first dose of CPI-613. Post-study survival, medical and cancer treatment information will be collected bimonthly via telephone contact after treatment termination.

RR is defined as % of patients who experienced a Complete Response (CR) or Partial Response (PR). CR and PR are based on Response Evaluation Criteria in Solid Tumor (RECIST) Version 1.1 Eisenhauer et al. 2009). The best response recorded from the start of the treatment until Disease Progression (DP) will be considered.

PFS will be determined from the first dose of CPI-613 to DP or death due to any cause, assessed up to 3 years after the first dose of CPI-613.

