6.0 TREATMENT WITH CPI-613

CPI-613 will be administered to patients as shown in Table 6-1 (below). Briefly, a treatment cycle is 4 weeks, with CPI-613 given on Days 1 and 4 of the first 3 weeks. CPI-613 will also be given for 5 consecutive days a week before the start of Cycle 1, and this Pre-Cycle 1 treatment will only be given once in each patient. During Pre-Cycle 1 and each treatment cycle, patients will be treated with CPI-613 at the same dose, unless dose modification is warranted (see Section 6.2).

Table 6-1: Administration of CPI-613 in Patients with Advanced Cholangiocarcinoma

Treatment Cycle			Administration of CPI-613
	Week	Day	
Pre-Cycle 1 (1 week)	1	1	2-hr IV infusion via a central venous catheter
		2	2-hr IV infusion via a central venous catheter
		3	2-hr IV infusion via a central venous catheter
		4	2-hr IV infusion via a central venous catheter
		5	2-hr IV infusion via a central venous catheter
Cycle 1 (4 weeks)	1	1	2-hr IV infusion via a central venous catheter
		4	2-hr IV infusion via a central venous catheter
	2	1	2-hr IV infusion via a central venous catheter
		4	2-hr IV infusion via a central venous catheter
	3	1	2-hr IV infusion via a central venous catheter
	4	2-hr IV infusion via a central venous catheter	
Cycle 2 (4 weeks)	1	1	2-hr IV infusion via a central venous catheter
		4	2-hr IV infusion via a central venous catheter
	2	1	2-hr IV infusion via a central venous catheter
		4	2-hr IV infusion via a central venous catheter
	3	1	2-hr IV infusion via a central venous catheter
	4	2-hr IV infusion via a central venous catheter	
Etc. up to a total of 12 cycles ^a			

hr = hour; IV = intravenous; min = minutes.

^a Additional cycles can be given if the investigator considers it beneficial to do so.

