For adverse events unrelated to serum creatinine elevation or reduction in renal function but are possibly related to CPI-613, the occurrence of Grade 1 toxicity does not generally require dose modification for subsequent doses for that patient. However, if Grade 2 toxicity (other than alopecia and nausea) probably related to CPI-613 develops, treatment is to be withheld and can resume only after the Grade 2 toxicity has been reduced to Grade 1 or below, and the dose level for subsequent doses for that patient will be reduced by 25% of the dose at which such Grade 2 toxicity occurs. Grade 2 alopecia and nausea do not require withholding treatment or dose reduction. If Grade 3 or 4 toxicity probably related to CPI-613 develops, dosing of CPI-613 of that patient will be withheld and the patient shall be monitored for recovery from, and reversibility of, such Grade 3 or 4 toxicity. To resume treatment with CPI-613 for a patient who has had CPI-613-related Grade 3 or 4 toxicity, the Grade 3 or 4 toxicity must be reduced to Grade 1 or below, and the dose level for subsequent doses for that patient will be reduced to 50% of the dose at which such Grade 3 or 4 toxicity occurs.

For adverse events related to creatinine elevation or reduction in renal function that are possibly related to CPI-613, dosing of the patient will be withheld even if the severity level is Grade 2 or above. Treatment can resume only after the toxicity has been reduced to Grade 1. The dose level for subsequent doses for that patient will be reduced by 15% if the severity level is of Grade 1, by 25% for Grade 2 toxicity, and by 50% for Grade 3 or 4 toxicity.

Furthermore, if the toxicity possibly related to CPI-613 is acute renal failure and the severity level is Grade 3 or 4, further patient enrollment will be temporarily suspended in order to enable assessment of the following aspects of the trial and implementation of corrective measures or protocol amendment, and if necessary:

- compliance of the study sites and investigators to the study protocol
- evaluation of the appropriateness of the procedures for monitoring renal function

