For the time-to-event outcomes we will estimate survival curves for OS and PFS using Kaplan-Meier techniques. In addition, we will estimate the 6 month and 1-year OS and PFS rates for these participants. For response rate we will present the proportion of patients who are CR, PR, SD or PD. In addition, we will estimate the proportion of responders as the percent of patients who are CR or PR. For this rate we will also include a 95% confidence interval.

We will also examine toxicities for these 10 patients by looking at each toxicity identified earlier in the protocol by grade.

Sample Size Considerations

Since this is a pilot study we do not anticipate having statistical power to detect specific effects, however with this sample size we will be able to estimate the response rate using a 2-sided 95% confidence interval with an interval that will extend no more than 0.31 from the observed

Comprehensive Cancer Center of Wake Forest University
A Pilot Study: Open-Label Clinical Trial of CPI-613 in Patients with Advanced Bile Duct
Cancers
CCCWFU # 59212

response rate.

Comprehensive Cancer Center of Wake Forest University
A Pilot Study: Open-Label Clinical Trial of CPI-613 in Patients with Advanced Bile Duct
Cancers
CCCWFU # 59212

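### Routine CT scans follow cycle number while PFS runs in calendar time: if toxicity holds shift cycles, about 10 to 13 days of delay puts the second scan past the 6-month PFS landmark

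*Combined protocol and SAP*

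**What the plan says.** - **Clock for PFS.** Section 5.1.3: "PFS will be determined from the first dose of CPI-613 to DP or death due to any cause".
- **Planned estimate.** Section 9.0, Proposed Analyses: "we will estimate the 6 month and 1-year OS and PFS rates for these participants". The analytic sample is the ten Cohort 5 patients.
- **Scan times.** Table 5-2, footnote 4, puts the first scan "during week 4 (preferably Wednesday or later) of cycle 3 for all patients", and then: "For patients without progression, perform during week 4 of cycles 6, 9, and 12". Section 5.1.3 also counts in cycles and gives months only as an approximation.
- **Progression on the cycle 3 scan.** Footnote 4 puts the rescan in week 4 of cycle 5. It then adds a three-monthly rule for patients still on study after cycle 5.
- **Holds.** Section 6.2, for Grade 2 non-renal toxicity probably related to the drug, other than alopecia and nausea: "treatment is to be withheld and can resume only after the Grade 2 toxicity has been reduced to Grade 1 or below". Related Grade 3 or 4 toxicity, and renal events of Grade 2 or above, also lead to a hold. No maximum length is given.

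The plan gives no calendar window for scans, does not define 6 months in days, has no rule for late assessments, and does not say whether a hold lengthens the cycle or whether withheld doses are simply skipped.

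**The concern.** Progression that only imaging can show is dated at the scan that finds it. If scan dates move with treatment delays, a patient with more toxicity is scanned later and has a later recorded progression date. Between the first and second scans this matters most for the 6-month rate, because the second scan is due shortly before that landmark. Once it slips past, the only on-treatment scan before 6 months is the one at about day 88.

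The triggers for a hold are broad. Of the six adverse events marked as expected in Section 8.1, only nausea is exempt at Grade 2. Section 9.0 intends these data to inform likely effect sizes for later work, so a 6-month PFS rate that depends partly on toxicity-driven scan timing would carry forward. The point concerns patients still on treatment.

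**Working it through.** **Inputs.** Pre-Cycle 1 lasts one week (Section 6.0: "CPI-613 will also be given for 5 consecutive days a week before the start of Cycle 1"). Cycle length is 28 days (Section 6.0: "a treatment cycle is 4 weeks, with CPI-613 given on Days 1 and 4 of the first 3 weeks"). Scans fall on day 3, 4 or 5 of week 4 (Table 5-2). The analysed cohort has n = 10, all with Pre-Cycle 1 (Section 9.0). The plan states no scan days, so it has no figure to reproduce. I take 6 months as 365.25/2 = 182.6 elapsed days and also check 180 and 184.

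**On-time scan days** (first dose = study Day 1; cycle k; d = 3, 4, 5): day = 7 + 28(k − 1) + 21 + d

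- k = 3: 7 + 56 + 21 + d = 87 to 89
- k = 6: 7 + 140 + 21 + d = 171 to 173
- k = 9: 7 + 224 + 21 + d = 255 to 257
- k = 12: 7 + 308 + 21 + d = 339 to 341

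**Slack before 6 months at cycle 6.** Study day D is D − 1 elapsed days.

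- 182.6 elapsed days: 182.6 − 172 = 10.6 to 182.6 − 170 = 12.6
- Landmark placed at study Day 183: 183 − 173 = 10 to 183 − 171 = 12
- 180 elapsed days: 8 to 10; 184 elapsed days: 12 to 14

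A delay exactly equal to the slack puts the scan on the landmark; passing it takes slightly more. Twelve days over six cycles averages two days per cycle.

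**Less exposed quantities.**

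- 1-year rate (cycle 12 scan): 365.25 − 340 = 25.3 to 365.25 − 338 = 27.3 days of slack.
- Cycle 5 rescan after progression at cycle 3 (days 143 to 145): 182.6 − 144 = 38.6 to 182.6 − 142 = 40.6 days.
- Cohort 1 has no Pre-Cycle week, so 7 more days of slack, and it is outside the analytic sample.

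**Effect per affected patient.** 1/10 = 10 percentage points, absent earlier censoring.

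**Illustrative total.** Assumptions, none from the documents: exponential PFS with median m = 2 to 6 months; scans at 87 and 171 elapsed days; a share q = 0 to 0.5 of events recognised without a scan; the first scan on time; delay unrelated to progression. With S(t) = 2^(−t/(30.44m)), the expected 6-month estimate is:

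- second scan on time: S(171) − q[S(171) − S(182.6)]
- second scan after the landmark: S(87) − q[S(87) − S(182.6)]

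| m (months) | q | On time | All late | Rise (points) |
|---|---|---|---|---|
| 2 | 0 | 14.3% | 37.1% | 22.8 |
| 2 | 0.5 | 13.4% | 24.8% | 11.4 |
| 3 | 0 | 27.3% | 51.7% | 24.4 |
| 3 | 0.5 | 26.2% | 38.3% | 12.1 |
| 4 | 0 | 37.8% | 60.9% | 23.1 |
| 4 | 0.5 | 36.6% | 48.1% | 11.5 |
| 6 | 0 | 52.3% | 71.9% | 19.6 |
| 6 | 0.5 | 51.1% | 60.9% | 9.8 |

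If 10% of patients are delayed enough, the rise is 0.10 × (9.8 to 24.4) = 1.0 to 2.4 points. If 30% are, it is 0.30 × (9.8 to 24.4) = 2.9 to 7.3 points.

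**The case against.** **A hold may not move the scan.** No section says that it does. Section 6.0 and Table 5-2 fix each cycle at four weeks; if withheld doses are skipped on that calendar, scans stay put and there is no bias. This stands as a limit on the claim. The heading of Section 6.2 refers to delay and its text to resuming treatment, which favours a shift, but the wording fits either reading for a patient held mid-cycle. A reader might infer that holds necessarily postpone scans; the documents do not establish that.

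**Footnote 4 already has a calendar rule.** The three-monthly rule is calendar-based. It follows the sentence on patients with progression at cycle 3 and most naturally belongs to them, but its wording is not limited to them. Its scope is unclear.

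**The effect is confined.** Deaths are dated when they occur, and symptoms and performance status are checked in each treatment week. Only progression visible solely on imaging, in a patient with enough accumulated delay, is misplaced. This stands. Section 6.1.2 also reports no significant adverse effects at or below the maximum tolerated dose in earlier trials, so long holds may be uncommon.

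**Nothing is decided on PFS.** It is a secondary endpoint, described in ten patients of a single arm. A few points is small beside the sampling error at that size. This limits the importance but does not remove a systematic, one-directional error that is cheap to avoid.

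**Conclusion.** The concern holds in conditional form. PFS is in calendar time, routine scans are in cycle time, and holds are unlimited in length. If a hold shifts the cycle, about 10 to 13 days of cumulative delay moves the Cohort 5 cycle 6 scan past 6 months. Each patient whose progression in that interval is found only by imaging then adds about 10 points to the 6-month rate.

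A reader might go further and infer that toxicity will inflate the reported rate by a known or large amount. The documents do not support that: they give no hold frequency or duration, so the number of affected patients cannot be computed. The 1 to 7 points above rest on an assumed 10 to 30% of patients delayed, an assumed median and an assumed share of clinically recognised progression. The 1-year rate has about 25 to 27 days of slack and is less exposed. Importance is low to moderate.

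**What to change.** In Table 5-2, footnote 4, and Section 5.1.3, set the routine scans for patients without progression by calendar time from first dose, irrespective of dose holds, at the times the schedule already implies:

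- with Pre-Cycle 1: weeks 13, 25, 37 and 49
- Cohort 1: weeks 12, 24, 36 and 48

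Give each a window, for example ±1 week; week 25 plus one week ends on day 26 × 7 = 182. Define 6 months in days; if 180 elapsed days (study day 181) were chosen, that window would have to close one day earlier.

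Leave the rescan after progression on the cycle 3 scan tied to the two additional cycles. Sections 1 and 5.1.3 use those cycles to judge pseudoprogression, and a fixed date could force that judgement too soon. State which patients the three-monthly rule covers and from what date it counts.

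If the sponsor prefers to keep scans tied to cycles, the minimum is to state whether a hold shifts the cycle and to report actual scan dates alongside the 6-month rate.

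**Cost.** A wording change in two places. A patient on schedule has the same scans, at the same times. CA-19-9 and the optional samples carry the same footnote and would move with the scan. The downside is that after a long hold a scan, and the response assessment made from it, may follow fewer doses than planned.
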